Inclusion/Exclusion criteria	
Inclusion Criteria:
 
 • Patient must be 18 years of age or older • Patient must have been treated with either Knee Spanning or Damage Control FastFrame External Fixation System according to the indications stated in this protocol* 
Exclusion Criteria:
 
 • Patient has an active or suspected infection • Conditions that limit the patient's ability and/or willingness to follow instructions during the healing process • Inadequate skin, bone, or neurovascular status • Patient is a prisoner • Patient is pregnant and/or breastfeeding • Patient is a known current alcohol and/or drug abuser in the opinion of the Investigator • Patient has a mental or neurologic condition that will not allow for proper informed consent and/or participation in follow-up program in the opinion of the Investigator 
*EEA Indications (a subset of the cleared US indications): The FastFrame External Fixation System – Knee Spanning Kit is indicated for use in treatment of long bone (distal femur, proximal tibia) fractures. Specifically, the system is intended for temporary stabilization of open or closed fractures about the knee, typically in the context of polytrauma or where open or alternative closed treatment is undesirable or otherwise contraindicated.
 
The FastFrame External Fixation System – Damage Control Kit is indicated for use in treatment of mid-shaft long bone (femur, tibia) fractures. Specifically, the system is intended for temporary stabilization of open or closed fractures of the femur and tibia, typically in the context of polytrauma or where open or alternative closed treatment is undesirable or otherwise contraindicated.

Study Design	Prospective enrollment, prospective follow-up, single cohort study
Clinical Phase	Postmarket
Sample Size	Considering a 95% device success rate (5% device related complications) and a 10% non-inferiority margin, 60 subjects with a follow-up are required. With an estimated lost to follow-up/subject withdrawal rate of 10%, 66 subjects will have to be enrolled.
Length of Study	3 years (2 years of enrollment plus follow-up until exchange with another device) A follow-up visit will be completed at the time of exchange from FastFrame System to another device. Typically, this exchange occurs 2 to 4 weeks after injury.

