The management of orthopaedic polytrauma patients has developed greatly since the 1970s, when patients were deemed incapable of undergoing surgery³. In recent years, the use of temporary stabilization of fractures has been used with the goal to decrease operative time³, blood loss³, and the “second hit” inflammatory response from definitive surgical fixation². External fixators, a type of device intended for temporary stabilization, are typically made up of a combination of a frame, clamps, pins, and bars that properly stabilize and support the injured limb¹. In order for this stabilization to occur, the fractured bones are adjusted to reduce the fracture and the bars are connected to maintain the reduction¹. Unlike typical external fixators, the FastFrame External Fixation frames are pre-assembled and are designed for simplicity in the operating room. Each kit includes clamp bodies, pins, and telescoping bars that allow for proper reduction and rigid external fixation. This study will document the clinical outcomes of

trauma patients who require the use of the FastFrame External Fixation System - Knee Spanning and Damage Control kits legally manufactured by Zimmer, Inc.

VI. Study Objectives

The objective of this observational, prospective study is to confirm safety and performance of the FastFrame External Fixation System and corresponding instrumentation. The endpoints are defined to include the following:

Primary Endpoints

- Frequency and incidence of device-related adverse events and device deficiencies before the FastFrame External Fixation System is exchanged by another device (i.e. plates, screws, etc.). Refer to Section XII for additional details related to adverse event classification and device deficiencies.

Examples of device-related adverse events and device deficiencies include:

- Pin breakage and/or loosening requiring surgical intervention (i.e. pin removal or exchange) before planned exchange of the complete frame by another device
- Frame component failure (i.e. loosening, breakage, etc.) leading to clinically unacceptable loss of stability requiring unplanned readjustment or replacement of the frame

Secondary Endpoints

- Adverse events that occur between application of the FastFrame External Fixation System and exchange with another device that do not fall within the primary endpoint. Refer to Section XII for additional details related to adverse event classification.

VII. Study Design and Endpoints

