All surgeries will take place following the standard, approved surgical technique. During the course of the surgery, a **Surgical Device** CRF must be completed documenting the part and lot numbers of the implants. The FDA cleared or other local government regulatory body approved instructions for use and surgical technique must be followed for this product. Please refer to the latest versions of these documents on the Zimmer Biomet website, contact your local Clinical Study Manager, or contact a Zimmer Biomet sales associate for additional details. The following operative data will be collected on the following CRFs:

- **Operative Record**
- **Surgical Device**
- **Protocol Deviation, if applicable**
- **Adverse Event Report, if applicable**
- **Physician Imaging Assessment**
- **Photographs of study device in two (2) planes (A/P and lateral)**

Photographs will be stored in the Subject Binder as part of their casebook. Please write the Subject Case ID Number, Subject Initials, and Date (YYYY-MM-DD) on the photographs. If an adverse event occurs, an **Adverse Event Report** CRF will also be completed. See Management of Incurrent Events for additional details. Reason(s) for study completion must be documented on the **Study Completion** CRF.

Post-Operative Follow-Up Procedure

Post-operative clinical assessment will be conducted at the device exchange follow-up visit after the procedure. The device exchange of a FastFrame External Fixation Kit typically occurs 2-4 weeks after surgery. The following

CRFs will be collected at the follow-up visit when the study device is removed from the subject:

- **Physician Follow-Up Assessment**
- **Protocol Deviation, if applicable**
- **Adverse Event Report, if applicable**
- **Physician Imaging Assessment, if required**
- **Photographs of study device in two (2) planes (A/P and lateral), if required**
- **Study Completion**

Subjects will be followed post-operatively until the FastFrame External Fixation Kit is exchanged with another device or unless the primary endpoint is reached prior. Unless the study is otherwise closed, data will continue to be collected until the subject completes the study per the protocol, voluntarily withdraws from the study, is withdrawn from the study by the Investigator, is lost to follow-up, undergoes revision to remove a study device (does not include device removal as part of standard treatment), or expires.

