Study subject participation is expected to end upon completion of the subject's device exchange follow-up visit unless the subject voluntarily withdraws from the study, is withdrawn from the study by the Investigator, is lost to follow-up, undergoes an unplanned revision to remove a study device, or expires. Reason(s) for study completion must be documented on the **Study Completion CRF**.

If the Sponsor decides to terminate the study early, the Sponsor will inform the Investigators of the reason for early study termination. It is the responsibility of the Investigators to inform their IRB as applicable according to local and national laws/regulations.

Modification of the Protocol

All amendments to this clinical protocol shall be agreed to by the Sponsor and be recorded with a justification for the amendment prior to implementation. Approval of the applicable IRB must be obtained prior to implementation, if required according to the local and/or national laws/regulations.

XII. Safety Management – Medical Events/Adverse Events

Adverse events are required to be reported on the **Adverse Event Report CRF**. The completed **Adverse Event Report** CRF must be submitted to the Sponsor in a timely manner. The Investigator or Designee will also promptly provide the Sponsor with any additional requested information required for the Sponsor to comply with regulatory requirements. If applicable per their reporting requirements, the Investigator or Designee will also report applicable adverse event(s) to their IRB.

The following definitions are from ISO 14155:2020 and Regulation (EU) 2017/745: Safety reporting in clinical investigations of medical devices.

Classification of the Event

Adverse Event (AE):

An adverse event is any untoward medical occurrence, unintended disease or injury, or untoward clinical signs (including abnormal laboratory findings) in subjects, users or other persons, whether or not related to the investigational medical device and whether anticipated or unanticipated.

Note 1: This definition includes events related to the investigational medical device or the comparator.

Note 2: This definition includes events related to the procedures involved.

Note 3: For users or other persons, this definition is restricted to events related to investigational medical devices or comparators.

Serious Adverse Event (SAE):

A Serious Adverse Event is any adverse event that:

- a. led to death.

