Statistical methodology will consist of summarizing collected data descriptively. Categorical data (i.e., gender or race) will be summarized using counts and percentages, and 95% CI, over the time periods of interest. Continuous data, such as age, will be summarized by using means, medians, standard deviation, minimum, maximum, and 95% CI over the time periods of interest. Implant survival will be summarized using a Kaplan-Meier method and presented with rates (as percentages) and confidence intervals.

Sample Size

Calculation of sample size is based on previously published literature involving longitudinal data collection on temporary external fixation. Assuming a power level of 80% and an alpha level of significance of 0.05 ($\alpha = 0.05$), calculations were performed in order to determine the sample size needed for study significance using the following hypothesis test:

The hypothesis will be tested by the exact binomial test:

$$H_0: E_1 - E_0 \leq -\delta E$$

$$H_a: E_1 - E_0 > -\delta E$$

where:

$E_0 = 95\%$, the expected success rate

E_1 = the success rate in the FastFrame System treatment group

$\delta E = 0.10$, non-inferiority margin

In addition, one-sided 95% exact confidence Interval (CI), lower limit of the success rate, will be calculated.

Based on the hypothesis test above, 60 subjects will provide approximately 80% power for the one-sided exact binomial test at 0.05 significant level. The sample size was calculated using SAS for Windows version 9.4.

It was determined that the complication rate of devices comparable to the FastFrame External Fixation System is approximately 5%. Utilizing this figure, the power, and alpha level of significance, a sample size total (without any subjects becoming lost to follow-up) of 60 was obtained. Finally, in order to maintain a sample size large enough for statistical significance an estimated, 90% subject return rate is assumed for the duration of the device exchange follow-up visits. These lost to follow-up patients increase the sample size requirements to 66 subjects (after rounding up).

Visit	Subjects remaining in the study
Baseline	66
Follow-Up	60

XVI. Quality Control & Quality Assurance

The study is conducted in accordance with the Declaration of Helsinki and the ISO 14155:2020 and Regulation (EU) 2017/745.

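### Kaplan-Meier implant survival does not suit a temporary frame: planned exchange is a competing event, so cumulative incidence of unplanned removal should replace it

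*Combined protocol and SAP*

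**What the plan says.** The only time-to-event analysis in the combined protocol and SAP is one sentence under General Statistical Methods (section XV): "Implant survival will be summarized using a Kaplan-Meier method and presented with rates (as percentages) and confidence intervals". It gives no event, time origin, censoring rule, reporting time, or handling of planned exchange and death. No endpoint listed in the Synopsis or section VI uses it.

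Other sections describe how a frame's use ends:

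- Post-Operative Follow-Up Procedure (section X): "Subjects will be followed post-operatively until the FastFrame External Fixation Kit is exchanged with another device or unless the primary endpoint is reached prior".
- Timing is counted from injury in the Synopsis ("Typically, this exchange occurs 2 to 4 weeks after injury") and from surgery in section X ("The device exchange of a FastFrame External Fixation Kit typically occurs 2-4 weeks after surgery"). The Data Collection Overview (section IV) puts follow-up at Day 14-28.
- Section X lists among the reasons for ending data collection that a subject "undergoes revision to remove a study device (does not include device removal as part of standard treatment), or expires". Study Termination (section XI) has similar wording: "is lost to follow-up, undergoes an unplanned revision to remove a study device, or expires".

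The primary endpoint is "Frequency and incidence of device-related adverse events and device deficiencies before the FastFrame External Fixation System is exchanged by another device". For the formal comparison, section XV says: "The hypothesis will be tested by the exact binomial test".

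**The concern.** Kaplan-Meier treats a censored subject as still able to have the event later. A subject whose frame has been exchanged as planned cannot have that frame fail. Exchange is therefore a competing event, and it is the intended end of use for every frame, although death, withdrawal or loss may come first.

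The sentence can be carried out in two ways, and neither gives the risk of failure before exchange, which is how the study frames its question:

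- **Planned exchange censored.** The curve describes failure had no frame been exchanged. After Day 14 the risk set empties by design, so one late failure can move the estimate by many points.
- **Any removal counted as the event.** The curve describes when surgeons exchange frames and ends at about 0%.

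At stake is a percentage, published in a report meant to confirm safety and performance, that readers may take as the share of frames that failed in use.

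**Working it through.** **The plan's own figure.** No Kaplan-Meier figure is stated. The stated figure is 60 subjects with about 80% power for the one-sided exact binomial test at 0.05, with success 95% expected and 95% - 10% = 85% under the null. The smallest qualifying cut-off is 56 successes of 60: P(X ≥ 56 | 0.85) = 0.0424 and P(X ≥ 56 | 0.95) = 0.820. The figure reproduces and does not involve the Kaplan-Meier curve.

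**Direction.** At a failure time with d failures among n at risk, 1-KM rises by S_KM × d/n. The cumulative incidence (Aalen-Johansen) rises by S_all × d/n, where S_all also falls at each planned exchange. Since S_all ≤ S_KM, 1-KM is never below the cumulative incidence of the same event. The two are equal until the first exchange.

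**Size under stated assumptions.** The 5% is the plan's expected complication rate, used here as failure before exchange. Exchange uniform over Day 14-28 and a constant hazard h are assumptions. Solving for 5% gives h ≈ 0.00245 per day.

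- 1-KM at day t = 1 - e^(-ht).
- Cumulative incidence at Day 28 = 1 - (e^(-14h) - e^(-28h))/(14h) = 1 - (0.96628 - 0.93370)/0.0343 = 0.050.
- Cumulative incidence at Day 21 = 1 - [(e^(-14h) - e^(-21h))/(14h) + 0.5e^(-21h)] = 1 - [(0.96628 - 0.94985)/0.0343 + 0.47493] = 0.046.

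| Day | 1-KM | Cumulative incidence | Gap (points) |
|---|---|---|---|
| 14 | 3.4% | 3.4% | 0 |
| 21 | 5.0% | 4.6% | 0.4 |
| 28 | 6.6% | 5.0% | 1.6 |

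Simulated trials of 60 agree: mean 1-KM at Day 28 was 6.4% to 6.8% across runs, against 5.1%.

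**Sensitivity, at about 5% failure before exchange (simulated, n = 60).**

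| Assumption | Read at | 1-KM | Cumulative incidence |
|---|---|---|---|
| All failures before Day 14 | Day 28 | 5.0% | 5.0% |
| Rising hazard (Weibull, shape 3), exchange Day 14-28 | Day 28 | 9.9% | 5.0% |
| Constant hazard, exchange uniform Day 1-42 | End of curve | 9.5% | 5.1% |
| Constant hazard, exchange log-normal (median 20 days, sigma 0.4) | Day 28 | 6.5% | 4.7% |

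**Instability of the tail.** Take 60 subjects, 3 failures (5.0%) and 57 exchanges evenly spaced over Day 14-28. Only the failure days change:

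| Failure days | Numbers at risk | KM at Day 28 | 1-KM |
|---|---|---|---|
| 3, 7, 12 | 60, 59, 58 | 59/60 × 58/59 × 57/58 = 0.950 | 5.0% |
| 7, 16, 24 | 60, 51, 18 | 59/60 × 50/51 × 17/18 = 0.910 | 9.0% |
| 20, 24, 27 | 36, 19, 6 | 35/36 × 18/19 × 5/6 = 0.768 | 23.2% |
| 7, 16, 27.9 | 60, 51, 2 | 59/60 × 50/51 × 1/2 = 0.482 | 51.8% |

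The cumulative incidence is 5.0% in all four.

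**Any removal as the event.** Under the constant-hazard, uniform-exchange assumptions, simulated survival is about 97% at Day 14, 47% at Day 21 and 0% at Day 28.

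**The case against.** The strongest reply is that this is one descriptive sentence, tied to no endpoint, and that any distortion is conditional. Most of that stands.

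- Overstatement requires that exchange is censored, that failures occur after exchanges begin, and that the curve is read as the risk in use. If all failures precede the first exchange there is none.
- If planned exchange is independent of failure risk, censoring it validly estimates failure had the frame stayed on. That is a reasonable durability question, but the plan does not ask it.
- Sections X and XI separate unplanned revision from removal as part of standard treatment. This makes removal-as-event the less natural reading. Those passages govern when follow-up stops, however, and section XV does not adopt them.
- Large effects depend on where the curve is read. Under the log-normal assumption, mean 1-KM is about 11% and about 18% of trials exceed 15%, but only at the end of the curve. About 20% of exchanges in that distribution fall after Day 28, outside the typical window the plan gives.

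A reader might infer that the Kaplan-Meier figure will systematically exceed the primary failure rate. The documents do not support that. The primary endpoint covers all device-related adverse events and deficiencies. Unplanned removal is only part of it, so its rate could well be lower. The inequality holds only when both estimates use the same event.

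The reply does not remove the mismatch between method and device. The plan sets no reporting time that would keep readers out of the unstable tail.

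**Conclusion.** The point holds as a choice of the wrong summary for this device, and it is worth correcting. With planned exchange censored, 1-KM answers a hypothetical question, cannot fall below the cumulative incidence of the same event before exchange, and becomes unstable as exchanges proceed. The expected gap is nil at Day 14 and about 1.6 points at Day 28. This rests on assumed uniform exchange over Day 14-28, a constant hazard and 5% failure before exchange. Late failures or widely spread exchange times widen it.

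A reader might also infer that the study's conclusion is biased. It is not: the exact binomial test, its one-sided confidence limit and the sample size of 60 do not use this curve. Nor is a survival of about 0% the expected result, since it follows only from the less natural definition of the event.

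**What to change.** Replace the Kaplan-Meier sentence in section XV with:

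*Time from application to first unplanned frame removal or replacement for a device-related cause will be summarised by the cumulative incidence function (Aalen-Johansen), with planned exchange or removal and death as competing events and withdrawal or loss to follow-up censored, reported at Day 14 and Day 28 with numbers at risk and 95% CIs.*

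Readjustment of the frame is left out on purpose. It is not loss of the implant and would create a new endpoint. Because follow-up may stop when the primary endpoint is reached, the text should also say how a subject is counted whose first such event is not a removal.

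A simpler alternative is to delete the sentence and report the proportion with unplanned device-related removal or replacement, with its exact interval. With no loss to follow-up, the cumulative incidence at the end of follow-up equals that proportion.

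The cost is one sentence and a standard analysis. It needs the same dates as the curve it replaces and no change to the sample size. The small downside is that the result is no longer directly comparable with published Kaplan-Meier implant-survival figures.

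### Minor arithmetic slip: 60 subjects at a 90% return rate need 67 enrolled, not 66, but the 59 that 66 would leave still give over 80% power

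*Combined protocol and SAP*

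**What the plan says.** The Sample Size row of the Study Synopsis (Section III) reads: "Considering a 95% device success rate (5% device related complications) and a 10% non-inferiority margin, 60 subjects with a follow-up are required". It continues: "With an estimated lost to follow-up/subject withdrawal rate of 10%, 66 subjects will have to be enrolled".

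Section XV, Sample Size, gives the same figures in more detail. On power: "60 subjects will provide approximately 80% power for the one-sided exact binomial test at 0.05 significant level". On the number before attrition: "a sample size total (without any subjects becoming lost to follow-up) of 60 was obtained". On attrition: "90% subject return rate is assumed for the duration of the device exchange follow-up visits". On enrolment: "These lost to follow-up patients increase the sample size requirements to 66 subjects (after rounding up"). A small table below then shows 66 at baseline and 60 at follow-up.

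Two other places matter. The Lost to Follow-up paragraph in Section XI says that such patients are not replaced. Section VIII defines the primary analysis population as all enrolled subjects who meet the eligibility criteria, without requiring a follow-up visit.

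**The concern.** Three stated figures do not fit together: 60 needed at follow-up, 90% returning, and 66 enrolled. To end with 60 after 10% loss, the 60 must be divided by 0.90. The stated 66 is what comes from multiplying 60 by 1.10, a common shortcut that falls slightly short. The remark about rounding up does not fit that shortcut, because 60 × 1.10 is already a whole number.

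A gap of one subject would usually not deserve comment. It does here because the planned test is an exact binomial test, whose permitted number of failures changes in steps, and one of those steps lies between 58 and 59 subjects. The plan states no permitted number of failures for any analysed number, and with no replacement nothing restores the count if losses run slightly above plan.

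**Working it through.** **Inputs**
- Expected success rate 95% and margin 0.10 (Sections III and XV), so the null success rate is 0.95 − 0.10 = 0.85.
- One-sided exact binomial test at 0.05, target power 80% (Section XV).
- 60 subjects at follow-up, 90% return, 66 enrolled (Sections III and XV).
- No replacement (Section XI).

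**Step 1: reproduce the plan's 60.** For n subjects, let f be the largest number of failures with P(X ≤ f) ≤ 0.05 when X ~ Bin(n, 0.15). Power is P(X ≤ f) when X ~ Bin(n, 0.05). At n = 60, f = 4, the size is 0.0424 and power is 82.0%. The plan's approximate 80% at 60 is therefore right.

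**Step 2: enrolment**
- 60 / 0.90 = 66.67, rounded up to 67.
- 60 × 1.10 = 66.0, which matches the stated figure.
- 66 × 0.90 = 59.4, so 59 whole subjects.
- The table's 66 to 60 is a loss of 6/66 = 9.1%.
- 67 × 0.90 = 60.3, so 67 does deliver 60.

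**Step 3: what one subject does to the test**

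| Analysed n | Failures allowed | Size | Power |
|---|---|---|---|
| 57 | 3 | 0.0210 | 68.2% |
| 58 | 3 | 0.0187 | 67.0% |
| 59 | 4 | 0.0469 | 82.8% |
| 60 | 4 | 0.0424 | 82.0% |
| 61 | 4 | 0.0382 | 81.1% |
| 62 | 4 | 0.0345 | 80.2% |
| 66 | 4 | 0.0226 | 76.6% |
| 67 | 4 | 0.0203 | 75.7% |

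Going from 60 to 59 does not lower power. Going from 59 to 58 lowers it by 82.8 − 67.0 = 15.8 points. The step also shows in the planned one-sided 95% exact lower limit: with 4 failures it is 85.2% at 59 (above 85%, pass) and 84.9% at 58 (fail).

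**Step 4: attrition as a random number.** This step adds two assumptions: each subject returns independently with probability 0.90, which the documents do not state, and only subjects with follow-up are analysed. The number analysed is then Bin(66, 0.90) or Bin(67, 0.90), and the Step 1 power is averaged over it.

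| Enrolled | P(58 or fewer) | P(fewer than 60) | Average power |
|---|---|---|---|
| 66 | 1 − 0.661 = 34% | 1 − 0.506 = 49% | 77.0% |
| 67 | 1 − 0.776 = 22% | 1 − 0.646 = 35% | 78.0% |

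If instead exactly 59 return, power is 82.8%. The gap between 82.8% and 77.0% is the effect of the randomness assumption, not of the slip.

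**The case against.** The strongest reply is that nothing is lost. At 59 analysed, which is what the plan's own return rate gives, power is above both the target and its value at 60. That stands. A reader might infer that enrolling 66 leaves the study short of its planned power, and the documents do not support this: Section XV attaches its power statement to 60 subjects, where it is correct, and it also holds at 59.

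A second reply is that the step between 58 and 59 comes from the discreteness of the exact test and exists whatever the enrolment. That also stands. Correcting 66 to 67 raises average power by only one point, from 77.0% to 78.0%, under an independence assumption that is not in the plan. It would be wrong to present the step as a consequence of the slip. It is a reason to state the pass rule.

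Third, the origin of 66 is inferred. No formula is given, and 59/0.90 = 65.6 also rounds up to 66. The text names 60 as its base, however, so the figures disagree however 66 was reached.

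Fourth, Section VIII may put every enrolled eligible subject in the denominator. Under that reading the 58/59 step is not reached: with all 66 analysed, at most 4 failures pass and power is 76.6%. This does not rescue the 66, because the Synopsis sizes the study on subjects with follow-up, but it does limit the working above to that reading.

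**Conclusion.** The concern holds as a minor arithmetic error. From the plan's own 60 and 90%, enrolment should be 67; the stated 66 is one short, and the follow-up row of 60 corresponds to 9.1% loss. The error alone costs no power (82.8% at 59, 82.0% at 60). The practical point is narrower: an eighth loss among 66, leaving 58, reduces the permitted failures from 4 to 3 and power to 67.0%, and the plan does not say so.

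The arithmetic in Step 2 rests only on stated figures. The power values rest on the stated test with 85% against 95%, and on analysing subjects with follow-up. The averages of 77.0% and 78.0% rest additionally on independent 10% loss and should carry that label wherever they are used.

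**What to change.** **Option without extra patients.** Keep 66 enrolled. Change the required number from 60 to 59 in the Synopsis and throughout Section XV (power statement, total before attrition, follow-up row of the table), so that 59/0.90 = 65.6 rounds up to 66. Changing the table row alone would leave it in conflict with the 60 stated elsewhere. Then add a sentence such as: *At 59 to 62 evaluable subjects, at most 4 failures pass (power 80% to 83%); at 58, at most 3 failures pass (power 67.0%).*

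The second half should name 58 only. Below 58, power is not constant: it is 68.2% at 57, 70.5% at 55 and 76.0% at 50, and at 49 three failures no longer pass (tail probability 0.0513). If smaller numbers are to be covered, tabulate them.

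**Alternative.** Keep 60 and state enrolment as 67 in the Synopsis (sample size and target population rows) and in Section XV (text and baseline row). The same sentence on permitted failures applies.

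Under either option, state whether subjects lost to follow-up count in the primary denominator, so that Section VIII and the sample size agree.

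**Cost.** A few corrected figures and one or two sentences. The first option adds no patients, the second adds one. The test, the margin and the significance level are unchanged.
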